## 7.0. STATISTICAL CONSIDERATIONS

As part of Preliminary Study 3, we have already created and successfully implemented a secure web-based system to capture the study data using the REDCap database management system, as well as a telephone log system and participant calendar that will enable the research coordinators to track and schedule participants' visits. We will review and process data using already-programmed multiple verification and edit-checking programs. We will also conduct rudimentary analyses to ensure that the data have been properly collected and to identify any outliers or errors.

Preliminary analyses: Prior to hypothesis testing, we will calculate coefficient alpha as a measure of internal consistency reliability on all multiple-item scales. Construct validity will be assessed by calculating Pearson or Spearman correlations between scales to determine if correlations are in the expected direction. We will assess multicollinearity between the scales for the mediators by examining the correlations above. If any pairwise correlations are 0.7 or higher we will not include both variables in a given model but fit separate models instead and acknowledge this issue in the interpretation. We will also compare the AME group to the attention control group with respect to demographic and baseline outcome variables using two-sample *t* tests, chi-square tests, or Fisher's

Exact tests as appropriate. We will control for any demographic variables that are not balanced in the models below (all models will adjust for baseline outcome). We will also control for site in all models.

**Main analyses:** For analyses below we will analyze as randomized and attempt to collect outcome data on non-completers, following the intent-to-treat principle. For Aims 1 and 2, each outcome will be modeled separately. Also we will model T2 separately from T3. Thus, there will be a total of 12 models in Aim 1 (6 outcomes x two time points). In Aim 2, two outcomes will be examined and 3 potential moderators at two time points for a total of 12 (2 outcomes x 3 moderators x 2 time points) models. For Aim 1, our primary goal is to test mediation effects. Mediation effects will be estimated in an ANCOVA setting, fitting the appropriate mediation models using MPlus and then testing indirect effects using the percentile bootstrap approach to estimate the indirect effect. The multiple mediation model with three-path mediation effects specifies that the intervention will act through the proximal and distal mediator on the outcome and also have a direct effect on the outcome. Each outcome model will have 6 key predictors (intervention, two proximal mediators, 3 distal mediators), and control for T1, age (3-5 years vs. 6-8 years), site, and any imbalanced baseline covariates found above (allowing for up to 6 imbalances). Thus we will have up to 15 variables in any model. For Aim 2, we will test moderation effects by including the appropriate interaction terms of the potential moderator (dichotomized at the median) with the intervention indicator (AME vs. attention control) in our models. For all models in Aims 1 and 2, we will assess goodness-of-fit (GOF) using standard GOF measures (comparative fit index, root mean square error of approximation, and root mean square residual). For Aim 3, an exploratory aim, we will use ANCOVA to compare changes in child symptom distress at T2 and T3 between intervention and control groups. In light of positive findings, we next will explore models as in Aims 1 and 2 to assess for potential mediation and moderation effects for this outcome.

**Missing data and multiple comparisons:** We will compare all baseline variables between subjects who drop out of the study and those who do not using two-sample *t* tests, chi-square tests, or their non-parametric equivalents as appropriate. MPLUS software will incorporate participants who drop out before completion by using the MPLUS imputation method to perform a bias adjustment for missing data under maximum likelihood estimation and the assumption that data are missing at random. If we find that missing data are not missing at random, we will use a pattern mixture modeling approach to address; however, based on our prior studies we expect limited attrition (<15%) and little to no missing data on instruments (<1%). As our primary outcomes are child (CHQ) and parent emotional/traumatic (POMS) distress and other outcomes are considered secondary, we do not plan on adjusting *p* value for multiple comparisons for the primary outcomes but will apply the Hochberg step-up procedure for the secondary outcomes.

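### Fitting mediators correlated at 0.7 or more in separate models lets each absorb the other's indirect effect whenever AME moves both

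*Combined protocol and SAP*

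**What the plan says.** Section 7.0, Main analyses, states the purpose: "For Aim 1, our primary goal is to test mediation effects". The default is one joint model per outcome and time point: "Each outcome model will have 6 key predictors (intervention, two proximal mediators, 3 distal mediators"). The three-path structure "specifies that the intervention will act through the proximal and distal mediator on the outcome and also have a direct effect on the outcome", and inference is by "testing indirect effects using the percentile bootstrap approach to estimate the indirect effect".

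The Preliminary analyses paragraph makes an exception. The correlations are obtained by "calculating Pearson or Spearman correlations between scales to determine if correlations are in the expected direction", and then: "We will assess multicollinearity between the scales for the mediators by examining the correlations above". The rule follows: "If any pairwise correlations are 0.7 or higher we will not include both variables in a given model but fit separate models instead". The only accompanying safeguard is to "acknowledge this issue in the interpretation".

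The plan does not say:
- whether the correlation is pooled over arms, taken within arm or adjusted for arm;
- at which time point it is taken;
- how mediation is decided once a pair has been split;
- what becomes of the three-path model if the split pair is one proximal and one distal mediator.

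**The concern.** Aim 1 asks which mechanisms carry the effect of AME. The tool that separates one mediator from another is mutual adjustment in a joint model. The rule removes that adjustment in the one situation where attribution is hardest, so the indirect effects from the split models suffer omitted-variable bias.

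The proximal pair is a plausible candidate. Child engagement and parent-child interaction are both coded from the Session 3 video (Sections 4.0 and 6.0) and both are named as direct targets of AME (Section 5.0). Study 3 in Section 1.0 reports significantly more of both. At stake is a conclusion that credits the wrong mechanism, which would then carry into refinement of the conceptual model and the design of later trials.

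**Working it through.** **Inputs from the documents.** 184 dyads recruited, 15% attrition, 156 retained, 78 per arm (Section 3.0). Check: 156/0.85 = 183.5, rounded up to 184; 2 × 78 = 156. The 0.7 threshold comes with no derivation.

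**Assumed inputs.** Section 1.0 says preliminary effect sizes exist but prints none, and no mediator correlation is given. I therefore assume a within-arm correlation r (mainly 0.7), an AME shift d in within-arm SD units on each mediator, and an outcome slope b for the active mediator M1. M2 is inactive.

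**1. Bias.** With M1 left out, the slope of M2 adjusted for arm is r × b. At r = 0.7 and b = 0.3 this is 0.21, where the truth is 0. The spurious indirect effect is d × r × b:
- d = 0.3: 0.063
- d = 0.5: 0.105
- d = 0.8: 0.168
- AME does not move M2 (d = 0 on M2): 0

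If both are active (b = 0.3 each, d = 0.5), each true indirect effect is 0.5 × 0.3 = 0.15. Each separate model gives 0.5 × (0.3 + 0.7 × 0.3) = 0.255. The two sum to 0.51 against a true total of 0.30.

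**2. How often M2 is declared a mediator.** Simulation of the two-mediator model, n = 156, r = 0.7, b = 0.3:

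| AME shift on both | Separate models | Both kept |
|---|---|---|
| 0.3 SD | 33% | 2–3% |
| 0.5 SD | 64% | 4% |
| 0.8 SD | 72% | 5% |

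If AME moves M1 only, the separate-model rate for M2 is about 3.5%. Repeat simulations of the 0.8 SD cell ranged from 71% to 78%, so these figures are good to within several points.

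The planned percentile bootstrap (600 trials, 500 resamples, b = 0.4, d = 0.5) gives the same picture: 80.7% against 4.0%. With b = 0.2 it is 36.2% against 4.7%.

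**3. Cost of keeping both.** VIF = 1/(1 − r²).
- r = 0.7: 1/0.51 = 1.96, so the SE is multiplied by 1.40.
- r = 0.9: 1/0.19 = 5.26, so the SE is multiplied by 2.29.

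Power for the truly active mediator (d = 0.8, b = 0.3) falls from about 96% to 74% at r = 0.7, and from about 95% to 35% at r = 0.9. At r = 0.7, d = 0.5 and b = 0.2, it falls from 60.5% to 33.7%.

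**4. Effect of pooling over arms, if that is what is done.** With 1:1 arms and equal shifts, pooled r = (r + d²/4)/(1 + d²/4).
- r = 0.60, d = 0.5: (0.60 + 0.0625)/1.0625 = 0.624.
- For d = 0.5, the rise is about 0.04 from r = 0.40 and 0.02 from r = 0.69.
- Lifting 0.60 to 0.70 needs d = 2 × √(0.10/0.30) = 1.15 on both mediators.
- If only one mediator moves, pooled r falls: 0.60/√1.16 = 0.557 at d = 0.8.

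**5. Sampling error of the trigger.** On Fisher's z scale the SE is 1/√153 = 0.081. A true correlation of 0.65 triggers the rule in about 13% of trials; a true 0.75 fails to trigger it in about 10%.

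**The case against.** **The plan discloses the problem.** It commits to acknowledging the issue, so it does not commit to confident attribution. That is fair, but disclosure changes neither the estimate nor the test, and no criterion is given for what may be claimed after a split.

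**The harm is conditional.** It needs the rule to fire and AME to move the inactive mediator. Both conditions stand. No correlation in the documents shows that the rule will fire. Beyond the proximal pair, the documents offer intent and hypothesis but no reported effect on the mediators.

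**Joint fitting is costly.** This also stands. The VIF of 1.96 applies only at the threshold, and well above it specific effects become nearly inestimable. In addition, the rate of 5% or less for the joint model assumes mediators measured without error. If the 0.85 inter-rater figure in Section 6.0 is treated as score reliability (an assumption), the joint model flags the inactive mediator in about 8–10% of trials.

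**The simulation is simpler than the plan.** It has two mediators acting directly on the outcome, where the plan has five in a three-path model. The percentages are illustrative. The bias formula shows the mechanism.

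**Two stronger readings are not supported.** A reader might infer that AME itself inflates the correlation used. The text never says the correlation is pooled, and family normalcy and self-efficacy are also measured at T1, where AME cannot act. Any inflation is small for shifts of 0.5 SD or less, and it reverses if only one mediator moves. A reader might also infer that the rule contradicts the six-predictor model. It is a prespecified exception to that model, so for the proximal pair there is no contradiction. For a proximal–distal pair the three-path model cannot be fitted as written, which is a gap to fill.

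**Conclusion.** The concern holds in conditional form. When the rule fires and AME moves both mediators, separate models cannot attribute the effect to either one. An inactive mediator is flagged in roughly one-third to nearly three-quarters of trials for shifts of 0.3 to 0.8 SD, and two active mediators are double-counted. The direction follows from the algebra; the size rests on the assumed correlation, slope and shifts. The condition on AME has documentary support for the proximal pair only. The unspecified basis of the correlation is a smaller, separate point of clarity. This should be changed, because it bears on the primary goal of Aim 1 and can be settled before analysis.

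**What to change.** In Section 7.0:
- Replace the split rule. Keep correlated mediators together in the planned joint model with free residual covariance.
- Report the joint (summed) indirect effect for a correlated pair as well as each specific one. State that the joint effect carries the conclusion when the specific effects are too imprecise to separate.
- Define the collinearity check as the within-arm (arm-adjusted) correlation or VIF at a stated time point, and use it only to flag imprecise specific effects.
- Show single-mediator models, if wanted, as descriptive and not specific to either mediator.

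This needs analysis wording only, with no new data. The price is the wider intervals and lower power for specific effects shown above. At correlations near 0.9 the trial may be able to say that the pair mediates, but not which member does.

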## 6.0. MEASURES AND DATA COLLECTION INSTRUMENTS

All measures reflect careful consideration of psychometric properties, sensitivity to change, and response burden. See Appendix 1 for measures and additional psychometrics.

Variable(s)	Measure	# Items	Reliability Evidence	Admin. Schedule	Completed By
Antecedent Factors					
Demographics -parent/child age, parent gender, SES, parent education	Family Information Form	3	N/A	T1	Parent
Prior Distress w/ Hospitalization -parent/child	Prior Illness Experiences Scale (PIES) Abbreviated PTSD checklist (PCL-S)	13 6	.78† .94†	T1 T1, T2, T3	Parent Parent
Disease Characteristics Treatment Characteristics	Diagnosis and Treatment Form Intensity of Treatment Rating Scale Medication Data Form	2 1 7	N/A .95* N/A	T3 T3 T1, T2, T3	Evaluator Oncologist Evaluator
Proximal Mediators					
Child Engagement Parent-Child Interaction	Behavioral Coding Form Behavioral Coding Form	N/A N/A	.85* .85*	Session 3 Session 3	Trained Coder Trained Coder
Distal Mediators					
Family Normalcy Perspective	Family Management Measure (FaMM) Family Life Difficulty Subscale	14	.90†	T1,T2,T3	Parent
Parent Self-Efficacy	Parental Beliefs Scale (PBS)	20	.85†	T1,T2,T3	Parent
Independent Music Play	Parent Report	2	N/A	Sessions 2/3; T2	Parent
Child Outcomes					
Child Emotional Distress	CHQ – Mental Health Subscale	16	.81†	T2, T3	Parent
Child Physical Symptom Distress	Edmonton Symptom Assessment System (ESAS)	3	.69-.80†	T1, T2, T3	Parent
Child Quality of Life	KINDL R	20	.89†	T1, T2, T3	Parent
Parent Outcomes					
Parent Emotional and Traumatic Stress Symptoms	Profile of Mood States-Short Form (POMS) Impact of Events Scale-Revised (IES-R)	37 22	.99** .84-.91†	T1,T2,T3 T1, T2, T3	Parent Parent
Parent Quality of Life	Index of Well-being	9	.93†	T1, T2, T3	Parent
Parent/Child Outcomes					
Family Function	(FACES II)	30	.90†	T1,T2,T3	Parent

†Cronbach's alpha; \*inter-rater reliability; \*\*correlation with POMS

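### Aim 1 mediation models: covariates are admitted by arm imbalance, which cannot detect mediator-outcome confounding, and the collected baseline scores of two distal mediators are, on the natural reading, left out of the outcome equation

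*Combined protocol and SAP*

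**What the plan says.** All references are to the combined protocol and SAP.

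- **Purpose (7.0, Main analyses).** "For Aim 1, our primary goal is to test mediation effects". The structure is a chain from arm to proximal mediator to distal mediator to outcome: "The multiple mediation model with three-path mediation effects specifies that the intervention will act through the proximal and distal mediator on the outcome". Indirect effects are tested by percentile bootstrap.
- **Covariates (7.0, Main analyses).** "Each outcome model will have 6 key predictors (intervention, two proximal mediators, 3 distal mediators"; in addition the models "control for T1, age (3-5 years vs. 6-8 years), site, and any imbalanced baseline covariates found above (allowing for up to 6 imbalances". The plan totals this: "Thus we will have up to 15 variables in any model".
- **How imbalances are found (7.0, Preliminary analyses).** The arms are compared "with respect to demographic and baseline outcome variables". Then: "We will control for any demographic variables that are not balanced in the models below (all models will adjust for baseline outcome". That last clause is the only explanation of what T1 means in the covariate list.
- **What is collected (6.0, measures table).** The self-efficacy row reads "Parental Beliefs Scale (PBS) 20 .85† T1,T2,T3 Parent". The family normalcy measure (FaMM, Family Life Difficulty subscale) has the same schedule. The other three mediators (child engagement, parent-child interaction, independent music play) have no T1 score.
- **Confounding (5.0, Study Design).** The randomised control group is the stated protection against confounding among intervention, mediators and outcomes. Section 7.0 names no mediator-outcome confounder set and no sensitivity analysis for unmeasured confounding.

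**The concern.** An indirect effect is a product of paths. Randomisation makes the arm-to-mediator path unconfounded. It does nothing for the path from mediator to outcome, because families are not randomised to self-efficacy or to a sense of normalcy. A parent who starts with high self-efficacy will tend to have high self-efficacy at T2, and may also have lower distress later for reasons that precede the intervention. If the starting level is not in the outcome equation, the T2 score can take the credit.

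Comparing arms is the wrong way to choose covariates for that path. What matters is whether a variable is related to both mediator and outcome, and it can be so while perfectly balanced between arms. At stake is the inference that Aim 1 exists to make: a claim that AME works through a given distal mediator, when that mediator has no effect on the outcome.

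**Working it through.** **1. The plan's own count.** 6 key predictors + T1 (1) + age (1) + site (1) + 6 imbalances = 15, as stated. If T1 also covered T1 FaMM and T1 PBS, it would be 6 + 3 + 1 + 1 + 6 = 17. So 15 is consistent with a single T1 term. It is not proof, because the count takes site as one variable. Three sites (5.0, Setting) need two indicators, giving 16; four sites (4.0) need three, giving 17.

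**2. What the imbalance screen can do.** Assume a 5% threshold (none is stated). Under randomisation any baseline variable is then selected about 5% of the time, however strongly it confounds. Even if T1 FaMM and T1 PBS were both screened, the chance that neither enters is 0.95 x 0.95 = 0.90, taking them as independent. In a one-mediator simulation with a confounder effect of 0.3 or 0.4 on both mediator and outcome, the screen lowered false mediation only from 16.4% to 16.0% and from 48.3% to 46.1%.

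**3. Hand check of the bias.** Assume T1-T2 correlation r = 0.5 for PBS, correlation 0.4 between T1 PBS and T1 outcome, a direct effect g of T1 PBS on the later outcome, and a true T2 PBS effect of zero. Given T1 outcome, the variance of T1 PBS is 1 - 0.4² = 0.84. Ignoring the other mediators, the T2 PBS coefficient in the outcome equation is about

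g x (r x 0.84) / (r² x 0.84 + 1 - r²) = g x 0.42 / 0.96 = 0.44g,

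that is 0.04, 0.09 and 0.13 at g = 0.1, 0.2 and 0.3, where the truth is zero. At r = 0.6 the multiplier is 0.504 / 0.942 = 0.53, so greater stability means more bias.

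**4. Simulation of the full chain.** From the documents: N = 156 (78 per arm). Assumed: arm effect on the proximal mediators 0.3-0.8; proximal-to-distal effect 0.3 or 0.5; r = 0.5; T1 FaMM-PBS correlation 0.5, each 0.4 with T1 outcome; residual correlation 0.4 among the proximal and among the distal mediators; effect of T1 outcome on the later outcome 0.4; all true distal effects zero. Mediation through PBS is declared when arm-to-proximal, proximal-to-PBS and PBS-to-outcome are all significant at 5%. Ranges cover the path values and two scalings of the outcome residual (total outcome variance 1, or residual variance 1).

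| Direct effect of T1 PBS on outcome | Planned covariates | T1 FaMM and T1 PBS in both equations |
|---|---|---|
| 0 | 2-6% | 2-6% |
| 0.1 SD | 3-10% | 2-6% |
| 0.2 SD | 5-23% | 2-6% |
| 0.3 SD | 11-45% | 2-6% |

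Adding the T1 scores to the mediator equations only leaves the planned-model rates essentially unchanged, since the bias arises in the outcome equation.

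**5. Check with the plan's test.** In a variant with independent distal residuals, at g = 0.2 with both path effects 0.5, the percentile bootstrap gave 22.9% without and 3.4% with the T1 scores (joint test 22.1% and 4.6%). With both path effects 0.3 it gave 8.2% and 1.5% (joint test 10.1% and 2.0%).

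**6. Power cost.** If the T1 scores have no direct effect on the outcome, adding covariates that are strongly correlated with the T2 mediators costs precision. For a true distal effect of 0.3, power falls by about 7-17 points at r = 0.5-0.6 and by 22-26 points at r = 0.7.

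**The case against.** **The omission is inferred.** T1 stands unqualified in the covariate list, and the count of 15 treats site as one variable, so it is weak evidence of what T1 contains. Hypothesis 1.1 treats normalcy and self-efficacy as effects to be explained, so adjusting for baseline outcome could put T1 FaMM and T1 PBS in the mediator equations. The imbalance route refers to baseline covariates, which is wider than demographics. All this stands as a reason to call it the natural reading and not a certainty. It does not rescue the plan: adjustment in the mediator equations alone does not remove the bias, and entry by chance imbalance is not planned adjustment.

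**The size is assumed.** Only N comes from the documents. Inflation needs T1 self-efficacy or normalcy to affect the later outcome beyond T1 outcome. At 0 to 0.1 SD the rates stay near nominal, and the upper figures depend on residual scaling. This stands.

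**The remedy costs power and is partial.** Both stand: the loss is material at N = 156, and three of the five mediators have no T1 score to adjust for.

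**The consequence is limited.** This is a mechanistic study meant to inform a later trial, and mediator-outcome confounding troubles every mediation analysis. That limits the severity. It does not justify leaving two scheduled baseline scores out of the model.

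**Conclusion.** The point holds as a should-fix. The screen cannot detect mediator-outcome confounders, and as most naturally read the outcome equation omits T1 FaMM and T1 PBS. The false-mediation rates above illustrate what follows if those scores have a direct effect of 0.1-0.3 SD. With no direct effect there is no inflation, and the documents do not say which case holds.

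A reader might infer more than this:

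- *That Aim 1 will report false mediation in up to 45% of cases.* The documents give no value for any parameter behind that figure except N.
- *That the prior-illness scale (PIES) and the abbreviated PTSD checklist (T1 PCL-S) must also be fixed covariates.* Section 5.0 (Conceptual Framework) links prior distress and traumatic stress symptoms to distress, which is a reason to consider them. No calculation here shows a benefit from adding them.
- *That the problem is worse for the child primary outcome because it has no baseline.* The measures table lists the CHQ at T2 and T3 only, while 7.0 says all models adjust for baseline outcome. Section 5.0 (Sources of Materials) has parents completing a set of measures at baseline, so this may be an omission from the table. It is a separate inconsistency and adds nothing to the size of this point.

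**What to change.** 1. Pre-specify T1 FaMM and T1 PBS, together with T1 outcome, age stratum and site, as fixed covariates in both the mediator and the outcome equations of every Aim 1 model, whatever the arm balance. Say explicitly what T1 denotes.
2. Either restate the maximum as 15 + 2 = 17 variables, or cut the imbalance allowance from six to four to stay at 6 + 1 + 1 + 1 + 2 + 4 = 15 (site counted once, as the plan does).
3. PIES and T1 PCL-S may be added on subject-matter grounds; if so, give the reason and update the count.
4. State that confounding remains possible for engagement, interaction and music play. If a residual-correlation sensitivity analysis is added, specify which mediator-outcome correlations vary, whether singly or jointly, and over what range.
5. Separately, reconcile the CHQ schedule in 6.0 with the baseline adjustment in 7.0.

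**Cost.** Items 1 to 4 need SAP wording and data already scheduled, with no new measurement. The real price is the power loss shown in step 6 of the working, which the SAP should acknowledge.

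### The primary child outcome (CHQ Mental Health) is scheduled at T2 and T3 only, yet every model must adjust for its baseline value; as written, 8 of the 24 Aim 1 and Aim 2 models cannot be fitted as specified

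*Combined protocol and SAP*

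**What the plan says.** The table in Section 6.0 has this row for the child's emotional distress: "Child Emotional Distress CHQ – Mental Health Subscale 16 .81† T2, T3 Parent". It is the only listed measure of that construct. Every other outcome in the table (ESAS, KINDL-R, POMS, IES-R, Index of Well-being, FACES II) is listed at T1, T2 and T3.

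Section 7.0 relies on a baseline score for each outcome in three places:

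- Preliminary analyses: "all models will adjust for baseline outcome".
- Preliminary analyses, on the balance check: the team will "compare the AME group to the attention control group with respect to demographic and baseline outcome variables".
- Main analyses: each Aim 1 outcome model will "control for T1, age (3-5 years vs. 6-8 years), site, and any imbalanced baseline covariates found above".

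The paragraph on missing data and multiple comparisons fixes the status of the CHQ: "our primary outcomes are child (CHQ) and parent emotional/traumatic (POMS) distress and other outcomes are considered secondary". For Aim 1, the Main analyses paragraph says that "our primary goal is to test mediation effects".

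Two places bear on whether the table cell is a slip. Section 5.0, Sources of Materials, has parents completing measures on three occasions, one of them baseline, but does not say which measures. Section 5.0, Study Design, refers to the Study Schema for assessment times, and Section 6.0 refers to Appendix 1 for the measures. Neither the Schema nor Appendix 1 was available for this review.

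**The concern.** The Section 6.0 schedule and the Section 7.0 model specification cannot both be followed for the CHQ. Nothing exempts the CHQ from baseline adjustment, and nothing names another T1 measure to take its place.

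Two things are at stake. First, if sites work from the table, the baseline score of a primary outcome is lost for good, and the analyst must choose a replacement model that was not pre-specified. Second, the loss differs by aim. In Aim 2 the comparison involves the randomised arm, so leaving out T1 costs precision but causes no bias in the AME effect. In Aim 1 the paths from engagement, family normalcy, self-efficacy and music play to later CHQ are observational. A child who is more distressed at the start may both engage less and score worse later. T1 CHQ is the planned control for that.

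**Working it through.** **1. Count the models.** The plan's figures reproduce: Aim 1 is 6 outcomes × 2 times = 12, and Aim 2 is 2 outcomes × 3 moderators × 2 times = 12, so 24 in all. The CHQ share is 1 × 2 = 2 in Aim 1 and 1 × 3 × 2 = 6 in Aim 2, so 8 of 24. Taking CHQ and POMS as the primary outcomes in both aims, it is 8 of 16 primary-outcome models.

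**2. Can the missing-data method rescue them?** No. Maximum likelihood under missing at random needs the covariate to be observed in some participants. T1 CHQ would be unobserved in all of them.

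**3. Precision.** The only input from the plan is 156 dyads at T3 (Section 3.0). Two-sided alpha of 0.05, 80% reference power and the correlation r between T1 and later CHQ are assumptions.

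- Detectable difference = (1.96 + 0.8416) × √[(4/156)(1 − r²)]
- Power without T1, where power with T1 is 80%: Φ(2.802 × √(1 − r²) − 1.96)

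| r | Detectable difference with T1 (SD) | Power without T1 |
|---|---|---|
| 0.3 | 0.428 | 0.762 |
| 0.4 | 0.411 | 0.728 |
| 0.5 | 0.389 | 0.679 |
| 0.6 | 0.359 | 0.611 |

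Without adjustment the detectable difference is 0.449 SD.

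**4. Aim 2 is partly protected.** In 4 of its 6 CHQ models (child or parent prior distress, × 2 times) the moderator already carries some baseline information. Let c be its correlation with T1 CHQ before the median split and k = c√(2/π). Assume that it relates to later CHQ only through T1 CHQ. Power is then Φ(2.802 × √[(1 − r²)/(1 − (rk)²)] − 1.96). For c from 0.3 to 0.7 this gives 0.764 to 0.774 at r = 0.3, and 0.620 to 0.662 at r = 0.6. The figures in step 3 are therefore an upper bound on the loss.

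**5. Aim 1 mediation.** This is a simplified simulation: one mediator, 156 dyads, true mediator effect on CHQ zero, percentile bootstrap (600 draws), 2,000 trials, simulation SE at most 0.011. T1 CHQ correlates r with later CHQ and q with the mediator. Entries are the false-positive rates for the indirect effect, without T1 CHQ, then with it.

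| AME effect on mediator | (r, q) = (0.3, 0.2) | (0.5, 0.3) | (0.6, 0.4) |
|---|---|---|---|
| 0.2 SD | 0.025 / 0.010 | 0.086 / 0.012 | 0.216 / 0.015 |
| 0.3 SD | 0.040 / 0.020 | 0.194 / 0.023 | 0.388 / 0.026 |
| 0.5 SD | 0.105 / 0.048 | 0.429 / 0.056 | 0.749 / 0.055 |

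Hand check of the bottom-right cell: without T1 the mediator coefficient picks up about r × q = 0.6 × 0.4 = 0.24. Its z is 0.24/√[(1 − 0.24²)/156] = 3.09, so it is significant with probability Φ(3.09 − 1.96) = 0.87. The AME-to-mediator z is 0.5/√(4/156) = 3.12, giving Φ(1.16) = 0.88. The product is about 0.76, close to the simulated 0.749.

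**6. How well would a substitute do?** The same simulation was run with one T1 proxy in place of T1 CHQ, for the three (r, q) pairs in the same order:

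| AME effect on mediator | Proxy correlates 0.7 with T1 CHQ | Proxy correlates 0.5 |
|---|---|---|
| 0.3 SD | 0.025 / 0.066 / 0.188 | 0.042 / 0.136 / 0.296 |
| 0.5 SD | 0.065 / 0.170 / 0.383 | 0.084 / 0.280 / 0.586 |

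A proxy helps but does not replace the baseline score.

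**The case against.** The strongest reply is that this is a slip in one cell. Section 7.0 relies on baseline outcomes three times, Section 5.0 has parents completing measures at baseline, and every other outcome row has T1. The same table also seems to differ from the text on another schedule: independent music play is listed at Sessions 2/3 and T2, while Section 5.0 (Study Design) gives sessions 2 and 3 and T3. The Study Schema or Appendix 1 may already show T1 for the CHQ. This reading is plausible and may well be right. It would reduce the remedy to a correction, but it does not remove the conflict: the statement in Section 5.0 does not name the CHQ, not every measure is given at every visit (PIES is T1 only), and sites may schedule from the table.

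The second reply is that the sizes rest on assumptions. That stands. The plan gives no power, correlations or path sizes; the 80% is a reference point chosen here. The plan's model has five mediators and three-path effects. A simple three-path version at the most adverse setting gave about 54% or 75% with an assumed mediator-to-mediator path of 0.2 or 0.3. The direction survives, but the rates do not transfer.

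The third reply is that a model without T1 can still be fitted and that randomisation protects the arm comparison. Both are true. But that model is not the one specified, and the protection does not extend to the mediator-to-CHQ paths.

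**Conclusion.** The concern holds. Section 6.0 and Section 7.0 contradict each other on a primary outcome, and confidence in that is high. Whether T1 CHQ is in fact uncollected is not known.

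If the table is followed, one third of the Aim 1 and Aim 2 models cannot be fitted as specified. The cost in Aim 2 is moderate and confined to precision. The cost in Aim 1 runs from no inflation above 5% to severe inflation, depending on how strongly initial distress drives both the mediators and later CHQ. The rating does not rest on any one of those rates. It rests on the conflict in the text, the primary status of the outcome and the fact that a baseline cannot be recovered later. This must be fixed, unless T1 CHQ is confirmed as already collected, in which case it is a table correction.

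**What to change.** Reconcile the Section 6.0 table with the Preliminary and Main analyses paragraphs of Section 7.0, in this order:

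1. Confirm whether T1 CHQ is collected, including against the Study Schema and Appendix 1. If it is, change the CHQ cell to T1, T2, T3. Cost: one cell.
2. If it is not, add the CHQ items to the existing baseline visit. Cost: 16 parent-completed items on top of 3 + 13 + 6 + 14 + 20 + 3 + 20 + 37 + 22 + 9 + 30 = 177 already scheduled at T1 (16/177, about 9% more), with no extra visit.
3. If T1 CHQ cannot be obtained, say in Section 7.0 that the CHQ models have no baseline-outcome term. Pre-specify one T1 measure already collected as a covariate in both the mediator and the CHQ equations. KINDL-R is one candidate. PIES is another, but it would overlap with the prior-distress moderators in 4 of the 6 Aim 2 CHQ models. One measure takes the place of the T1 term and leaves the stated maximum of 15 variables unchanged; if more are used, update that figure. Cost: one or two sentences. Given the residual error in step 6 of the working, this is a last resort. A sensitivity analysis for mediator-outcome confounding would be an optional addition.

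While the table is open, also reconcile the independent music play cell with the Study Design paragraph of Section 5.0.
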